10.13.4.1.3. Final Model

The model that has evaluated the impact of any key clinically relevant covariates (weight and other covariates) and adequately describes the observed data will be called the FINAL model and used for simulations.

The FINAL TQ POP PK model will be used to predict the systemic TQ exposure across various weight bands in pediatric population. The POP PK model based individual post-hoc TQ CL estimates will be utilized to calculate the individual TQ exposure $[AUC(0-\infty) = \text{Dose}/\text{CL}]$. At every interim analysis, the 95% prediction interval of AUCs based on the simulation with the population pharmacokinetic model will also be generated for the mid-point of each weight band (at a population level). See details in Section 3.1.

10.13.4.2. Interim TQ POP PK Analysis

Based on the data from the dose finding Phase 2B study in adult subjects with *P. vivax* malaria (TAF112582), initial POP PK modelling and simulation (M&S) exercise suggested that approximately 16 pediatric subjects would provide sufficient information to adequately characterize the TQ PK in this population. Hence the POP PK M&S activity will be undertaken after a total of at least 16 subjects have evaluable PK data or 12 months post study start whichever comes first. In

case these data are insufficient to adequately characterize the POP PK in the pediatric population, the sparse serial PK sampling will continue and the next M&S exercise will be performed after a total of at least 32 subjects have evaluable PK data or 24 months post study initiation, whichever comes first.

At every interim analysis, the 95% prediction interval of AUCs based on the simulation with the population pharmacokinetic model will be generated for the mid-point of each weight band (at a population level). If this interval lies within the AUC range of 55-162 $\mu\text{g}\cdot\text{hr}/\text{mL}$ for the mid-point of each weight band, serial (but sparse) sampling can be reduced for any subjects enrolled further. These bounds were chosen because 95% of adult subjects dosed with the efficacious dose of 300 mg TQ in part 1 of Study TAF112582 had an AUC that fell within this range and the lower bound is consistent with the clinically relevant breakpoint of 56.4 $\mu\text{g}\cdot\text{h}/\text{mL}$ for the adult Phase IIb data (TAF112582 Part1). Recruitment will continue for safety data accumulation with these subjects having a PK assessment at two timepoints.

The first set of 16 subjects to be enrolled in the study will be 2 or more years old. Based on the interim analyses of data from these 16 subjects, if TQ is well tolerated without any significant safety concern the enrolment will be opened to infants 6 months and older. If the 95% prediction interval of AUCs based on the simulation with the population pharmacokinetic model lies within the AUC range of 55-162 $\mu\text{g}\cdot\text{hr}/\text{mL}$ for the mid-point of each weight band, the dose strengths to be administered for the lower weight band subjects i.e. for infants 6 months to 2 years will be as listed in the protocol. Further original serial (but sparse) sampling may be limited to the subjects 6 months to 2 years.

If it is found that due to insufficient number of children being enrolled in the lowest weight band(s) the prediction intervals are wider in that lowest weight band, then further serial (but sparse) sampling may be limited to the children being enrolled in the lowest weight band. The analyses will then be repeated after next set of 4 subjects with serial PK sampling and so on until the TQ PK for that weight band are adequately characterized and the 95% interval within the targeted 55-162 $\mu\text{g}\cdot\text{hr}/\text{mL}$. Additionally, based on the available data post the two planned interim analyses, up to two samples will be collected in all children enrolled to provide data for the final population PK analysis of TQ to be conducted at the end of the study.

The second interim analysis will take place only if serial but sparse PK sampling is continued after the first interim analysis. At the end of any interim analysis, if the data and the M&S outcome reliably confirm the previously predicted TQ doses across various pediatric weight bands, or allow reliable estimation of TQ PK in the pediatric population, the PK sampling scheme in the subjects to be enrolled next may be modified or reduced as deemed appropriate.

At the end of any interim analysis, in the unlikely event of the data and the M&S outcome suggesting that the previously predicted TQ doses across various pediatric weight bands are grossly incorrect e.g. >2-3 fold off targeted exposure, existing pediatric PK data may be utilized to estimate a new dosing regimen. Exposure will be confirmed by continuing the sparse but serial PK sampling in the next set of 16 subjects with the new dosing scheme as deemed appropriate and necessary. One way to achieve this will be to modify the weight bands and TQ doses across the weight bands based on dose strengths. If the M&S outcome suggests that the previously predicted TQ doses across various pediatric weight bands are slightly off targeted exposure (e.g. <1.5 fold), the dosing may be continued as is, unless there are any safety concerns based on emerging data.

After study completion, the Final POP PK analysis will be performed to determine an appropriate dosing regimen across various weight bands in this population.

Any deviations from the analysis plan will be described in detail in the study report.

10.13.4.3. Final TQ POP PK Analysis

Upon completion of the study, final POP PK analysis will be undertaken. All PK evaluable data will be utilized for this analysis to confirm the dose regimen in the pediatric population across various weight bands. If the interim analysis demonstrate that the TQ PK was slightly different than previously predicted, M&S with the full dataset will be conducted to define the new dosage regimen across weight bands to ensure that the systemic TQ exposure across various weight bands in pediatric population is comparable to that in adult population. The simplest approach will be to modify the previously defined weight bands and the doses across these weight bands. The dosing scheme will be recommended in the study report.

Analysis of the TQ PK data from the pediatric study may also guide formulation of different dose strengths i.e. having fewer, more or different dose strengths than those used in the current pediatric study to support the TQ pediatric indication post approval. M&S will be undertaken to recommend the dose regimen with any new dose strengths across various pediatric population weight bands that provides exposure similar to that in adult population with the 300 mg TQ dose.

Any deviations from the analysis plan will be described in detail in the study report.

10.13.6. POP PK File Specification

10.13.6.1. Pop PK Dataset File Structure

The PME compliant file structure for pop PK is a space-delimited file with each row containing the following columns of information. This file will be provided within 5 days of DBF.

Records with CONC value of NS, IS or NR will be excluded from the dataset

Item Name	Description	Code	Derivation/Comments	Dataset
ID	NONMEM sequential number starting at 1 identifying each subject	00001 – 99999	Sequential identifier for each subject starting at 1.	
CENT	Centre Identification	1= Thailand - PPD 2= Madagascar - PPD 3= Peru - PPD 4= Thailand - PPD 5= Vietnam - PPD 6= Brazil - PPD 7= Colombia - PPD 8= Thailand - PPD 9= Thailand - PPD 10= Vietnam - PPD 11=USA - PPD 12= India- PPD 13= Philippines- PPD 14= Brazil- PPD 15=Ethiopia- PPD 16= Ethiopia- PPD 17=Cambodia PPD 18=Brazil- PPD 19=Peru PPD 20=SMIU Thailand- PPD 21=Thailand- PPD 22=Vietnam- PPD 23=Colombia- PPD 24=Colombia PPD	Additional centre numbers to be added based on where patients are recruited	
PT	Patient Identification Number		As per randomization; Retain all subjects with at least one measurable PK sample for the TQ analyte(s)	
STUDY		6= TAF113577		
TRTGRP	Treatment group for each study	24: TAF113577 arm		

Item Name	Description	Code	Derivation/Comments	Dataset
HEALTHY	Healthy volunteer or patient	1: Healthy volunteer 2: Patient	Studies 200951, 201780 and TAF114582 are all in Healthy volunteers (i.e., HEALTHY=1)	
DOSE	Dose amount (mg) for tafenoquine (TQ, SB252263)		Fill in the intended dose amount (mg) in all cells for each patient.	TQ
AMT	Dose amount (mcg) for tafenoquine	If EVID=1, AMT= Dose amt in mcg for tafenoquine If EVID=0, AMT= 0		TQ
DAY	Study day relative to the start of study		Day = day of study relative to the TQ dose	
DATE	Date of dose or sample collected.	MM/DD/YYYY		
TIME	Time of dose sample collected.	HH:MM (24 hr)		
RTLDD	Relative time of sample from most recent TQ dose (hr)	Numeric	If negative assign 0	
RTFD	Relative time of sample from first TQ dose (hr)	Numeric	If negative assign 0	
TQ	Plasma TQ concentrations (ng/mL)	Numeric If EVID = 1, DV = "." If CODE > 0 then DV = "." Else DV= conc. Value Where ADPC .AVAL ne "" or ADPC.ANL01FL="Y" Then TQ=ADPC.AVAL	3 decimal places.	TQ
LNTQ	Ln transformed Plasma TQ concentrations	Numeric	6 decimal places.	TQ
CODE	Drug concentration result code	0 = Measurable conc. 0 when EVID=1 1 = NQ/BQL 2 = NA/NR/NS/IS		
MDV	Missing Data Value (drug concentration)	1 = Yes, 0 = No If EVID = 1, MDV = 1 If EVID = 0 and CODE>0, MDV = 1 , otherwise MDV =0		
EVID	Event indicator (flag for NONMEM)	1 = Dose 0 = PK Sample		
VOMIT	Vomit within 60 min of dose	1 = Yes, vomited 0 = No 0 = PK observations -99=missing	-99 if missing in datasets	

Item Name	Description	Code	Derivation/Comments	Dataset
CNTY	Country	1=Brazil 2=Peru 3=Thailand 4=Colombia 5=Vietnam 6= India 7=USA 8=Ethiopia 9=Cambodia 10=Philippines	Other countries to be added where subjects recruited For the 114582, all are in the USA (as per the IB).	
AGE	Baseline Age of subject (yr)			
GEN	Gender of the Subject (1=M,2=F)	1=Male, 2 =Female		
RACE	Race of the Subject	1=White, 2=Black or african american, 3=Oriental or asian, 4= Hispanic, 5=Other 6= American indian or Alaska native 7= Multiple -99 =Missing		
WT	Baseline Weight of Subject (kg)			
BMI	Baseline Body mass Index (kg/m ²)		1 decimal	
PARA	Baseline parasitemia	1=Yes 0=No	-99 for all of these studies	
CONMEDS	Concomitant medications	Add if available as 1=Yes 0=No -99= Missing	1 – for subjects who have medications identified as being concomitant (could include subjects taking medications that are identified as starting prior and becoming concomitant) 0 – for subjects who do not take any concomitant medications (they may have had prior medications recorded only or no medications recorded at all) -99 is used when	

Item Name	Description	Code	Derivation/Comments	Dataset
FORMU	Formulation	1= Tablet150 3 = Tablet50	concomitant medication data is not collected in a study 1 = Tablet150 (150mg tablet strength) – only 300mg dose was administered with the 150mg tablet 3 = Tablet50 (50mg tablet strength) – all doses 200mg or less were administered 50mg tablets	
DUPLI	Duplicate records	DUPLI =1 for all concentrations DUPLI =2 for the duplicate concentration records for a specific date and time DUPLI=3 for samples with missing DATE/TIME records (but concentration is available) DUPLI=4 for a duplicate (second) dosing record where no vomiting of any doses occur	This variable is only provided for Study 582 Part 2 and Study 564 files. If no concentrations and time record, then we can exclude the records	

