6.1. Treatment Assignment

This is an open-label, single arm study, and all subjects will receive CQ and TQ. Subjects will be dosed based on weight, with the goal to achieve a median TQ exposure of 96 $\mu\text{g}\cdot\text{h}/\text{mL}$, the median exposure observed in adults following administration of a 300 mg dose of TQ. The TQ doses presented in [Table 2](#) below were selected using a population PK model based on adult data and incorporation of allometric scaling.

Table 2 Tafenoquine Dosing

Weights	Tafenoquine Dose^a	Dosing Regimen
>45 kg	300 mg	2 × 150 mg or 6 × 50 mg
>40–≤45 kg	300 mg	2 × 150 mg or 6 × 50 mg
>35–≤40kg	300 mg	2 × 150 mg or 6 × 50 mg
>30–≤35kg	200 mg	4 × 50 mg
>25–≤30 kg	200 mg	4 × 50 mg
>20–≤25 kg	200 mg	4 × 50 mg
>15–≤20 kg	100 mg	2 × 50 mg
>10–≤15 kg	100 mg	2 × 50 mg
≥5–≤10 kg	50 mg	1 × 50 mg

a. The TQ dose is based on achieving a target AUC(0–∞) of 96 µg.h/ml.

The single dose of TQ will be administered at the investigator site. Subjects >35 kg have the choice of taking the TQ adult tablet or the TQ pediatric tablet. All study medication should be administered with food. If the subject vomits within 1 hour following dosing, a repeat dose should be given. If a subject sequentially vomits two doses of study medication he/she will be considered intolerant to study medication. These subjects will be withdrawn from study medication and be given appropriate rescue medication as outlined in Section 6.9.1.2.

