6.1. Treatment Assignment

PREVIOUS TEXT

Table 10 Tafenoquine Dosing

Weights	Tafenoquine Dose^a	Dosing Regimen
>45 kg	300 mg	2 × 150 mg
>40–≤45 kg	300 mg	2 × 150 mg
>35–≤40kg	300 mg	2 × 150 mg
>30–≤35kg	200 mg	4 × 50 mg
>25–≤30 kg	200 mg	4 × 50 mg
>20–≤25 kg	200 mg	4 × 50 mg
>15–≤20 kg	150 mg	3 × 50 mg
>10–≤15 kg	150 mg	3 × 50 mg
≥5–≤10 kg	100 mg	2 × 50 mg

a. The TQ dose is based on achieving a target AUC(0–∞) of 96 µg.h/ml.

The single dose of TQ will be administered at the investigator site. Subjects >35 kg will take the TQ adult tablet. All study medication should be administered with food. If the subject vomits within 1 hour following dosing, a repeat dose should be given. If a subject sequentially vomits two doses of study medication he/she will be considered intolerant to study medication. These subjects will be withdrawn from study medication and be given appropriate rescue medication as outlined in Section 6.9.1.2.

REVISED TEXT

Table 11 Tafenoquine Dosing

Weights	Tafenoquine Dose ^a	Dosing Regimen
>45 kg	300 mg	2 × 150 mg or 6 × 50 mg
>40–≤45 kg	300 mg	2 × 150 mg or 6 × 50 mg
>35–≤40kg	300 mg	2 × 150 mg or 6 × 50 mg
>30–≤35kg	200 mg	4 × 50 mg
>25–≤30 kg	200 mg	4 × 50 mg
>20–≤25 kg	200 mg	4 × 50 mg
>15–≤20 kg	100 mg	2 × 50 mg
>10–≤15 kg	100 mg	2 × 50 mg
≥5–≤10 kg	50 mg	1 × 50 mg

a. The TQ dose is based on achieving a target AUC(0–∞) of 96 µg.h/ml.

The single dose of TQ will be administered at the investigator site. Subjects >35 kg have the choice of taking the TQ adult tablet or the TQ pediatric tablet. All study medication should be administered with food. If the subject vomits within 1 hour following dosing, a repeat dose should be given. If a subject sequentially vomits two doses of study medication he/she will be considered intolerant to study medication. These subjects will be withdrawn from study medication and be given appropriate rescue medication as outlined in Section 6.9.1.2.

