1.1. RAP Amendments

RAP Section	Amendment Details
Reporting and Analysis Plan_TAF113577_Final [11-APR-2017]	
Reporting and Analysis Plan_TAF113577_Amendment1_Final	
Section 2.3, Appendix 5.1 and Appendix	Dosing amended as per Protocol TAF113577 Amendment 2 (GSK Document number: 2014N207627_02)

15	
Section 4	Addition of Microbiological ITT population.
Appendix 2	Time and Events table amended as per Protocol TAF113577 Amendment 2 (GSK Document number: 2014N207627_02)
Appendix 3	Extended window for Study Day 1 to allow for screening procedures performed prior to Day 1.
Appendix 6.4	Updated censoring rule for subjects who demonstrated initial clearance to align with other studies in the project.
Appendix 10.12.7	Updated Pop PK file specification to align with current project standards.
Various	Minor typographical errors.
Reporting and Analysis Plan_TAF113577_Amendment2_Final	
Section 2.1 and Section 4	Addition of 2 analysis populations, the Screened and Enrolled populations.
Section 8.2.1, Section 10.6.3, Appendix 10.15.6 and Appendix 10.15.7	Amended definition for common AEs to those occurring in $\geq 10\%$ subjects (previously $\geq 5\%$)
Various	Minor clarifications and amendments.

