7. PRIMARY PK AND STATISTICAL ANALYSES

7.1. PK Analyses

7.1.1. Overview of Planned PK Analyses

The primary efficacy analyses will be based on the primary PK population, unless otherwise specified.

The primary population PK model based analysis to be performed at the end of the study may borrow some information from the POP PK model developed from the systemic TQ PK data from the dose ranging Phase 2B study (TAF112582). For example, the sparse sampling scheme in pediatric subjects is likely to be insufficient to independently characterize all the population PK parameters e.g. the absorption phase. Consequently, the information about absorption from the adult model will be used as prior information to feed into the pediatric PK model with the assumption that the absorption processes are similar in adults and pediatric subjects. Similarly, other information from the adult PK model may also be borrowed in the pediatric model (e.g., distribution). Additionally, any impact of formulation differences from Phase 2B study (TAF112582) and emerging data from the Part 2 of TAF112582 and TAF116564 may be utilized to inform model development. The pediatric population PK model will aim to reliably estimate the TQ clearance and thus the exposures in the pediatric population [$AUC(0-\infty) = \text{Dose}/CL$]. If data permit, other PK parameters such as apparent volume of distribution may also be estimated based on pediatric data; otherwise, the information will be borrowed from available adult data.

Such model based analyses utilizing prior information from the adult model may be implemented using one of the various options available within routinely used population PK software such as NONMEM [Beal, 2009] (ICON PLC, USA). The exposures in pediatric subjects across various weight bands will be simulated based on the population PK model developed from the pediatric PK data. The doses that provide target median exposures of 96 $\mu\text{g}\cdot\text{hr}/\text{mL}$ in each weight band will be estimated using the population PK model. The details of the approach are described in [Appendix 12](#) of this study reporting and analysis plan.

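### Does the formulation variable in the population PK file miscode children over 35 kg who take six 50 mg tablets?

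*SAP*

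**What the plan says.** SAP 10.13.6.1 lists the columns of the NONMEM file. For FORMU the code column reads "1= Tablet150 3 = Tablet50". The comment column repeats the two tablet strengths, adding for code 1 that "only 300mg dose was administered with the 150mg tablet" and for code 3 that "all doses 200mg or less were administered 50mg tablets".

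The current dosing rule is wider than the comment. Protocol 6.1, Table 2, gives the regimen in every row above 35 kg as "2 × 150 mg or 6 × 50 mg", and the text below it says "Subjects >35 kg have the choice of taking the TQ adult tablet or the TQ pediatric tablet". SAP 2.3 has the same regimen and the same choice. Until Amendment 2 the rule was "Subjects >35 kg will take the TQ adult tablet", as the amendment history in Protocol Appendix 10 shows.

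SAP 1.1 records "Dosing amended as per Protocol TAF113577 Amendment 2" against Section 2.3, Appendix 5.1 and Appendix 15. In the same SAP amendment the population PK file specification was updated, but to match project standards.

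On use of the variable, SAP 7.1.1 says that "any impact of formulation differences from Phase 2B study (TAF112582") and emerging data from two other adult data sets may inform model development. SAP 10.13.4.1.2 expects weight in the structural model and thinks other covariates unlikely because the study is small.

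**The concern.** The comment fits the dosing in force before Amendment 2, when 300 mg meant two adult tablets and every smaller dose meant 50 mg tablets. The choice above 35 kg was added later and the comment does not mention it. A programmer who took the comment as the derivation would set FORMU from DOSE, and each child on six 50 mg tablets would be recorded as an adult-tablet user.

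That would matter for two reasons. First, a dose-derived FORMU is the same variable as weight above 35 kg within this trial, so a formulation effect on bioavailability could not be told apart from the effect of weight. Second, children of 35 kg or less all take 50 mg tablets, so the heavier children on 50 mg tablets are the only ones in the trial who can separate the two, and they are the ones who would be miscoded. The primary endpoint is model-based AUC by weight band, and the weight exponent feeds the dose recommendation.

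**Working it through.** **1. The FORMU row against the regimens now allowed.**

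| Child | Tablets taken | Code by tablet strength | Does the comment contradict it? |
|---|---|---|---|
| 35 kg or less | 50 mg | 3 | No |
| Over 35 kg | 2 × 150 mg | 1 | No |
| Over 35 kg | 6 × 50 mg | 3 | No; the case is not mentioned |

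The comment on code 1 says the 150 mg tablet was used for no dose other than 300 mg. It does not say that every 300 mg dose used it. The comment on code 3 says doses up to 200 mg used 50 mg tablets. It does not say that only those doses did. Both hold under Amendment 2, and the third row follows from the code list alone. Miscoded as specified: 0.

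**2. If FORMU were nevertheless derived from dose.** The inputs are the weight distribution in Protocol Appendix 9 (log-normal, log-mean 3.36, log-SD 0.66, none below 5 kg) and an assumed share q of children over 35 kg who choose 50 mg tablets. The documents do not give q.

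- z = (ln 35 − 3.36)/0.66 = 0.296, so P(>35 kg) = 0.384. Dividing by 1 − 0.004 for the 5 kg limit gives 0.385. Appendix 9 states 36%.
- If all 60 children had the choice: 60 × 0.385 ≈ 23 over 35 kg. If only the 44 after the first 16 had it (assumption): 44 × 0.385 ≈ 17.
- Miscoded at q = 25% and 50%: about 6 and 12 of 23, or 4 and 8 of 17. At q = 0: none.

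Let a be the children over 35 kg on 150 mg tablets, b those over 35 kg on 50 mg tablets, and d those of 35 kg or less. The correlation of FORMU with weight over 35 kg is φ = ad/√[(a+b)·d·a·(b+d)]. Coded by tablet with 60 children, φ = 0.80 at q = 25% (a = 17, b = 6, d = 37) and 0.60 at q = 50% (a = 11, b = 12, d = 37). Coded by dose, φ = 1. Complete confounding therefore comes from the dose reading, or from no child choosing the 50 mg tablet.

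**3. What a formulation effect could do to the exponent.** No formulation ratio is in the documents, so 5%, 10% and 20% are illustrations. Attributing the whole step to the gap between the band mid-points of 27.5 and 47.5 kg gives ln(ratio)/ln(47.5/27.5) = 0.09, 0.17 and 0.33. But the exponent is fitted over the full weight range. The least-squares slope of a unit step at 35 kg on log-weight, under the truncated distribution above, is 0.593. (Without truncation it is the normal density at 0.296 divided by 0.66: 0.382/0.66 = 0.579.) The shifts become:

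- 5%: 0.0488 × 0.593 = 0.03
- 10%: 0.0953 × 0.593 = 0.06
- 20%: 0.1823 × 0.593 = 0.11

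These are about a third of the two-point figures. They also describe leaving formulation out of the model altogether, not miscoding some children.

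**4. Whether a formulation test above 35 kg would help.** The adult interval of 55–162 µg·h/mL (Protocol 4.5) implies a log-SD of ln(162/55)/(2 × 1.96) = 0.276. With an even split:

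- 11 against 12: SE = 0.276 × √(1/11 + 1/12) = 0.115, and exp(1.96 × 0.115) = 1.25.
- 8 against 9: SE = 0.276 × √(1/8 + 1/9) = 0.134, and exp(1.96 × 0.134) = 1.30.

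The 95% interval for the formulation ratio is the estimate multiplied and divided by about 1.25 to 1.30. Differences of 5% to 20% would not be resolved.

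**The case for a change.** The best case for a change is that FORMU is the only place in the file where tablet type survives. DOSE and AMT are the same for two 150 mg tablets and six 50 mg tablets, and no column records tablet count. The row names no source field, and its only explanatory text talks about dose. The products differ in more than strength: Protocol Table 1 describes a film-coated tablet and a fast-dispersing one. Appendix 9 names relative bioavailability and the allometric power among the parameters to estimate in children. Appendix 8 shows that the exponent matters, with nomogram error rising from 14.0 to 34.8 µg·h/mL when it moves from 0.522 to 0.750.

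Some of this stands. The comment is incomplete and out of step with SAP 2.3, and the specification does not say where tablet strength is read from. The rest does not amount to a fault in the plan. That FORMU is the sole carrier of tablet type is what its code list is for, and SAP 10.5.3 has data reported by the treatment actually received. The Appendix 8 comparison is a move of 0.228 in the exponent. By the slope in step 3 that would take a log ratio of 0.228/0.593 = 0.385, a bioavailability difference of about 47%. Appendix 8 itself puts much of that extra error in the 0–5 kg range, which is not treated. Overlap between formulation and weight also remains under correct coding, because the design gives every child of 35 kg or less the 50 mg tablet. Adult data, which SAP 10.13.2.3 allows to be pooled, could change that overlap; the documents do not allow this to be quantified.

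**Conclusion.** The concern does not hold as a fault in the analysis. FORMU is defined by tablet strength, so a child over 35 kg on six 50 mg tablets is code 3 and nothing is miscoded as specified. The miscoding and the complete confounding with weight both require a programmer to set the code list aside and work from dose. Taking FORMU from the tablet given is what the code column already says, so asking for it adds nothing. What is left is a comment that did not catch up with Amendment 2, a gap the programmer fills from the code list and the dosing table in SAP 2.3.

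The consequence is also small. Formulation enters the model only if the analysts choose to use it; if it is left out, its coding cannot touch AUC or the exponent. A required formulation test above 35 kg would rest on roughly 17 to 23 children and could not resolve the differences in question. These sizes assume the Appendix 9 weight distribution, an unknown uptake of the 50 mg tablet and an unknown formulation ratio; the reading of the code list depends on none of them.
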